10.11.9.2. Analysis Sets

For the purpose of analysis, the following analysis sets are defined for this substudy:

| Population | Description |
|------------------------------|---|
| Enrolled | All participants who have a signed ICD. |
| Randomized/assigned | All participants who are assigned a randomization number in the IWR system. |
| Evaluable immunogenicity | All eligible randomized/assigned participants who receive the study intervention to which they are randomized or assigned, have a valid and determinate immunogenicity result from the blood sample collected within an appropriate window, and have no other important protocol deviations as determined by the clinician. |
| All-available immunogenicity | All randomized/assigned participants who receive the study intervention with a valid and determinate immunogenicity result after vaccination. |
| Safety | All participants who receive the study intervention. |

10.11.9.3. Statistical Analyses

The SAP will be developed and finalized for this substudy before any analyses are performed and will describe the analyses and procedures for missing, unused, and spurious data. This section is a summary of the planned statistical analyses of the primary and exploratory endpoints.

10.11.9.3.1. General Considerations

All analyses will be performed separately for each age group (18-55 years of age, >55 years of age).

Refer to Section 9.3.1 for general considerations of statistical analyses.

A sensitivity analysis of GMR and difference in seroresponse rate for between-group comparison may be performed. The GMR and associated 95% CI will be calculated by exponentiating the difference in least-squares means and the corresponding CIs based on analysis of logarithmically transformed assay results using a linear regression model with terms of baseline assay results (log scale) and vaccine group. The difference in seroresponse rate between 2 vaccine groups and the associated 95% CI will be calculated using the stratified Miettinen and Nurminen method adjusting for the corresponding baseline assay result category (< median, \geq median).

10.11.9.3.2. Primary Endpoint(s)/Estimand(s) Analysis

| Endpoint | Statistical Analysis Methods |
|----------------|---|
| Safety | For each age group (18-55 years of age, >55 years of age): |
| | • Descriptive statistics will be provided for each reactogenicity endpoint for each vaccine group. Local reactions and systemic events from Day 1 through Day 7 after the study vaccination (where Day 1 is the day of vaccination) will be presented by severity and cumulatively across severity levels. Descriptive summary statistics will include counts and percentages of participants with the indicated endpoint and the associated Clopper-Pearson 95% CIs. |
| | • AEs and SAEs will be categorized according to MedDRA terms. Counts, percentages, and associated Clopper-Pearson 95% CIs of AEs within 1 month and SAEs within 6 months after study vaccination will be provided for each vaccine group. |
| | For sentinel-cohort participants 18 to 55 years of age: |
| | • Counts and percentages of participants with elevated troponin I levels before and 3 days after study vaccination, and associated Clopper-Pearson 95% CIs, will be provided for each vaccine group. |
| Immunogenicity | For each primary immunogenicity estimand described in Section 10.11.3, |
| | • GMRs and the associated 2-sided 95% CIs will be calculated using the method described in Section 9.3.1.2.3. |
| | • The percentages of participants with seroresponse for each group will be provided. The difference in percentages of participants with seroresponse and the associated 2-sided 95% CIs will be calculated using the Miettinen and Nurminen method (see Section 9.3.1.1). |
| | • Only participants with no serological or virological evidence (up to 1 month after receipt of 1 dose of study intervention given as a fourth dose) of past SARS-CoV-2 infection will be included in the analysis. |
| | • Superiority based on GMR will be established if the lower bound of the 2-sided 95% CI for the GMR is >1. Noninferiority based on seroresponse rate difference will be established if the lower bound of the 2-sided 95% CI for the difference in percentage is greater than -5%. |
| | • GMRs and the associated 2-sided 95% CI, and the difference in percentages of participants with seroresponse and the associated 2-sided 95% CIs, may be estimated using the sensitivity analysis approach specified in Section 10.11.9.3.1. |

10.11.9.3.3. Secondary Endpoint(s)/Estimand(s) Analysis

| Endpoint | Statistical Analysis Methods |
|----------------|---|
| Immunogenicity | For each secondary immunogenicity estimand described in Section 10.11.3. |
| | • GMR and the associated 2-sided 95% CIs will be calculated using the same method as for the primary immunogenicity objectives. |
| | • Noninferiority of anti–reference strain immune response based on the GMR will be declared if the lower limit of the 2-sided 95% CI for the GMR is greater than 0.67 (1.5-fold criterion) and the point estimate of the GMR is ≥0.8. |
| | • "Super" superiority of anti-Omicron immune response will be established if the lower bound of the 2-sided 95% CI for the GMR is >1.5. |
| | • GMRs and the associated 2-sided 95% CI may be estimated using the sensitivity analysis approach specified in Section 10.11.9.3.1. |

10.11.9.3.4. Exploratory Endpoint(s) Analysis

| Endpoint | Statistical Analysis Methods |
|----------------|---|
| Immunogenicity | GMTs and GMFRs of SARS-CoV-2 Omicron- or reference-strain- neutralizing titers |
| | Percentages of participants with seroresponse to Omicron- or reference-strain |
| | For each age group (18-55 years of age, >55 years of age): |
| | • GMTs at each time point and GMFRs of SARS-CoV-2 Omicron- or reference-strain—neutralizing titers from before the study vaccination to each subsequent time point after vaccination, along with the associated 2-sided 95% CIs, will be provided for each vaccine group using the statistical method described in Section 9.3.1.2.1 and Section 9.3.1.2.2. |
| | • The percentages of participants with seroresponse at each time point and the associated Clopper-Pearson 95% CIs will be provided for each vaccine group. |

| Endpoint | Statistical Analysis Methods | |
|-------------------------------|--|--|
| • | GMRs and the differences in percentages of participants with seroresponse between certain vaccine groups of interest may be calculated along with the associated 2-sided 95% CIs. | |
| | GMTs and GMFRs of SARS-CoV-2 reference-strain— and VOC-neutralizing titers for participants in the sentinel cohorts | |
| | For each age group (18-55 years of age, >55 years of age): | |
| | • GMTs at each time point and GMFRs of SARS-CoV-2 reference- strain— and VOC-neutralizing titers from before the study vaccination to each subsequent time point after vaccination, along with the associated 2-sided 95% CIs, will be provided for each vaccine group for sentinel cohorts. | |
| | GMTs for any VOCs not already specified | |
| | For each age group (18-55 years of age, >55 years of age): | |
| | • GMTs of reference-strain or VOC-neutralizing titers, along with the associated 2-sided 95% CIs, will be provided at specific time points for each group. GMFRs and GMRs of VOC-neutralizing titers to reference-strain—neutralizing titers may also be calculated along with the associated 2-sided 95% CIs. | |
| COVID-19 cases | Confirmed COVID-19 cases, confirmed severe COVID-19 cases, and strain sequencing of the COVID-19 cases will be summarized for each age group. | |
| Cell-mediated immune response | The cell-mediated immune response and additional humoral immune response parameters to the reference strain and Omicron will be summarized at each time point for the subset of participants with PBMC samples collected in each vaccine group for each age group. | |

10.11.9.4. Interim Analyses

No formal interim analysis will be conducted for this study. Statistical analyses will be carried out when the final data for specified objectives are available while the study is ongoing. The timing of these planned analysis and reporting events is described in the section below.

10.11.9.4.1. Analysis Timing

Statistical analyses will be carried out when the following data are available for each age group:

- Safety data through 1 month after study vaccination for each group in the sentinel cohorts.
- Immunogenicity data through 1 month after study vaccination for each group in the sentinel cohorts.
- Safety data through 1 month after study vaccination for each group in the expanded-enrollment cohort.
- Immunogenicity data through 1 month after study vaccination for each group in the expanded-enrollment cohort.
- Complete safety and immunogenicity analysis approximately 6 months after study vaccination for each group in the sentinel or expanded-enrollment cohorts.

Certain analyses may be combined as 1 regulatory submission report if the data become available around the same time. Additional analyses may be conducted if required for regulatory purposes. All analyses for the expanded-enrollment cohort conducted while the study is ongoing will be performed by an unblinded team.

10.11.9.4.2. Data Monitoring Committee or Other Independent Oversight Committee

The study will utilize an IRC and DMC. The IRC is independent of the study team and includes only internal members. The DMC is independent of the study team and includes only external members. The IRC and DMC charters describe the role of the IRC and DMC in more detail.

The responsibilities of the IRC are only for the sentinel cohort and will include:

• Review of all reported AEs, e-diary reactogenicity data, and troponin levels collected through Day 7 from all sentinel-cohort participants. This safety assessment will be conducted to determine if the study team may proceed with expanded enrollment of approximately 300 participants per group.

The DMC will be responsible for ongoing monitoring of the safety of participants in the study according to the charter.

The recommendations made by the DMC will be forwarded to the appropriate Pfizer personnel for review and final decision. Pfizer will communicate such decisions, which may include summaries of aggregate analyses of safety data, to regulatory authorities and investigators as appropriate.

10.11.9.5. Sample Size Determination

The sample size in each group is based on consideration of an acceptable safety database. For the >55-year age group, a random sample of 230 participants will be selected from each group in the expanded-enrollment cohort as an immunogenicity subset to evaluate the primary and secondary immunogenicity objectives. Assuming a 35% nonevaluable or prior infection rate, approximately 150 evaluable participants in each group will contribute to the primary immunogenicity evaluation.

Superiority and Noninferiority of Anti-Omicron Immunogenicity Objectives

For comparisons based on GMR, assuming common assay standard deviations of 1.05 in log scale based on data observed in the Phase 2 part of the C4591001 study for participants 56 years of age or older and adjusted for assay variability, if the true GMR is 1.5, with 150 evaluable participants, the study will have 91.5% power to demonstrate superiority. If the true GMR is 2.0, the study will have 65.7% power to declare "super" superiority using a 1.5-fold margin.

For comparisons based on seroresponse rate difference, if the seroresponse rate is 70% in the BNT162b2 OMI (30 μ g or 60 μ g) or bivalent BNT162b2 and BNT162b2 OMI (30 μ g or 60 μ g) group and 55% in the BNT162b2 30 μ g group, the study will have 94.9% power to demonstrate noninferiority using a 5% margin.

Noninferiority of Anti-Reference Strain Immunogenicity Objectives

For comparisons based on GMR, common assay standard deviations of 1.05 and a GMR of 1 are assumed for each comparison. With 150 evaluable participants and the stated assumptions for the GMR and standard deviation, the study has 90.9% power to demonstrate noninferiority based on the GMR using a 1.5-fold margin.

For safety outcomes, Table 14 shows the probability of observing at least 1 AE for a given true event rate of a particular AE, for various sample sizes. For example, if the true AE rate is 1%, with 300 participants in a vaccine group, there is 95% probability of observing at least 1 AE.

Table 14. Substudy E – Probability of Observing at Least 1 AE by Assumed True Event Rates With Different Sample Sizes

| Assumed True Event Rate of an AE | N=20 | N=300 | N=900 | N=1920 |
|-------------------------------------|-------|-------|-------|--------|
| 0.01% | 0.002 | 0.03 | 0.09 | 0.17 |
| 0.02% | 0.004 | 0.06 | 0.16 | 0.32 |
| 0.05% | 0.01 | 0.14 | 0.36 | 0.62 |
| 0.10% | 0.02 | 0.26 | 0.59 | 0.85 |
| 0.20% | 0.04 | 0.45 | 0.84 | 0.98 |
| 0.50% | 0.10 | 0.78 | 0.99 | >0.99 |
| 1.00% | 0.18 | 0.95 | >0.99 | >0.99 |
| 2.00% | 0.33 | >0.99 | >0.99 | >0.99 |

Table 14. Substudy E – Probability of Observing at Least 1 AE by Assumed True Event Rates With Different Sample Sizes

| Assumed True Event Rate of an AE | N=20 | N=300 | N=900 | N=1920 |
|-------------------------------------|------|-------|-------|--------|
| 5.00% | 0.64 | >0.99 | >0.99 | >0.99 |
| 10.0% | 0.88 | >0.99 | >0.99 | >0.99 |

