10.11.9.1.3. Multiplicity Adjustment

The primary and secondary immunogenicity objectives for participants >55 years of age will be assessed using the expanded-enrollment cohort.

The primary and secondary immunogenicity objectives for participants >55 years of age will be evaluated in sequential order as listed below using a 1-sided alpha of 0.025:

- Superiority in GMR and noninferiority in seroresponse rate for Omicron response: G4vG1A (OMI-60) → G6vG1A (bivalent-60) → G5vG1A (bivalent-30) →
- Noninferiority in GMR for reference strain response: G6vG1B (bivalent-60) → G5vG1B (bivalent-30) →
- "Super" superiority in GMR for Omicron response: G4vG1B (OMI-60) → G6vG1C (bivalent-60) → G5vG1C (bivalent-30) →
- Superiority in GMR and noninferiority in seroresponse rate for Omicron response: G3vG1A (OMI-30) → G3vG1B (OMI-30)

For objectives involving 2 hypotheses, hypotheses based on GMR and seroresponse rate difference will be assessed sequentially in the order as stated. Both hypotheses within the objective must be established before assessing the next objective in the sequence. Therefore, the overall type I error is fully controlled.

The immunogenicity objectives for participants 18 through 55 years of age are descriptive only; therefore, no multiplicity adjustment is applied.

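### Substudy E states single-comparison powers as the power of the study, although its both-hypotheses rule and fixed sequence leave the later objectives with clearly less

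*Protocol*

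**What the plan says.** Protocol section 10.11.9.5 bases group size on the safety database. It then defines an immunogenicity subset for those over 55 years: "a random sample of 230 participants will be selected from each group in the expanded-enrollment cohort". After a 35% loss, "approximately 150 evaluable participants in each group will contribute to the primary immunogenicity evaluation". On that basis it gives four powers:

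- GMR superiority, true GMR 1.5, SD 1.05 on the log scale: "the study will have 91.5% power to demonstrate superiority".
- 'Super' superiority against a 1.5-fold margin: "If the true GMR is 2.0, the study will have 65.7% power to declare" it.
- Seroresponse noninferiority, 70% against 55%, 5-point margin: 94.9%.
- Reference-strain noninferiority, true GMR 1, 1.5-fold margin: "With 150 evaluable participants and the stated assumptions for the GMR and standard deviation, the study has 90.9% power to demonstrate noninferiority".

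Section 10.11.9.1.3 sets the testing rule. The objectives "will be evaluated in sequential order as listed below using a 1-sided alpha of 0.025", in this order: G4vG1A, G6vG1A, G5vG1A (Omicron superiority plus seroresponse noninferiority for OMI-60, bivalent-60 and bivalent-30); G6vG1B, G5vG1B (reference-strain noninferiority); G4vG1B, G6vG1C, G5vG1C ('super' superiority); then G3vG1A and G3vG1B for OMI-30. For objectives with two hypotheses, "Both hypotheses within the objective must be established before assessing the next objective in the sequence". Section 10.11.9.5 mentions neither this joint requirement nor the sequence.

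**The concern.** The power section describes isolated tests, while the testing rule describes a chain. The sentence giving 90.9% for reference-strain noninferiority holds for a test that may never be reached: G5vG1B needs four earlier objectives, which contain seven hypotheses, to succeed first. G4vG1B, the first 'super' superiority test, needs five objectives and eight hypotheses.

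The bivalent-30 case rests on steps 3 and 5 together. Someone planning on section 10.11.9.5 would expect roughly nine chances in ten at each step. If the real chance of completing the package is nearer two in three, a chain broken by an OMI-60 or bivalent-60 test becomes a likely outcome that the plan does not prepare its readers for. It could then be misread as evidence against bivalent-30.

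**Working it through.** **Inputs from the protocol.** n = 150 per group (230 × 0.65 = 149.5); SD 1.05; 1-sided alpha 0.025; seroresponse 70% against 55% with a 5-point margin; GMR margins 1, 1.5 and 0.67; Group 1 as comparator throughout.

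**Assumptions not in the protocol.** All variant arms share one true Omicron GMR. The correlations between titer and seroresponse, and between Omicron and reference-strain titers, run from 0 to 0.8.

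**1. Reproducing the printed figures.** The standard error of a log GMR is 1.05 × √(2/150) = 0.1212. With a noncentral t distribution on 298 df:

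- Superiority: ln(1.5)/0.1212 = 3.344, power 91.5%.
- 'Super' superiority: ln(2.0/1.5)/0.1212 = 2.373, power 65.7%.
- Reference-strain noninferiority: −ln(0.67)/0.1212 = 3.303, power 90.9%.
- Seroresponse: SE = √[(0.70×0.30 + 0.55×0.45)/150] = 0.0552, and (0.15 + 0.05)/0.0552 = 3.62. The Wald approximation gives 95.2%; the Miettinen-Nurminen test gives 94.9%.

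All four match as single tests.

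**2. One objective.** With no correlation between its two hypotheses, G4vG1A succeeds with probability 0.915 × 0.949 = 0.868. Positive correlation raises this to about 0.89.

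**3. Down to step 5.** If all tests were independent, G5vG1B would have 0.868³ × 0.909² ≈ 0.54. The shared Group 1 makes the comparisons positively correlated, so the independent product is too pessimistic and simulation is needed.

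**4. Simulated power to declare each objective.** Participant-level data for Groups 1, 3, 4, 5 and 6, written criteria, written order. Separate runs differ by about one point.

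| Step | Objective | Printed | True Omicron GMR 1.5 | True Omicron GMR 2.0 |
|---|---|---|---|---|
| 1 | G4vG1A | 91.5% and 94.9% | 87-89% | 95% |
| 2 | G6vG1A | 91.5% and 94.9% | 78-82% | 91% |
| 3 | G5vG1A | 91.5% and 94.9% | 71-76% | 88% |
| 4 | G6vG1B | 90.9% | 65-74% | 80-82% |
| 5 | G5vG1B | 90.9% | 61-71% | 75-78% |
| 6 | G4vG1B | 65.7% | about 2% | 49-57% |
| 7 | G6vG1C | 65.7% | below 1% | 37-47% |
| 8 | G5vG1C | 65.7% | below 1% | 31-40% |
| 9 | G3vG1A | 91.5% and 94.9% | below 1% | 30-40% |
| 10 | G3vG1B | 65.7% | below 1% | 26-34% |

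The printed 91.5% assumes GMR 1.5 and the printed 65.7% assumes GMR 2.0, so each should be read against its own column. At GMR 1.5 the true ratio equals the 'super' margin, so the near-zero values there are expected.

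**5. Sensitivity.** A larger true GMR would probably bring a higher seroresponse rate. With 78% in the variant arms at GMR 2.0, G5vG1B is about 84-85%, G4vG1B 55-60%, G6vG1C 43-48% and G5vG1C 35-41%.

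**6. Extra condition.** The requirement on the point estimate (0.8) has no effect. A lower limit above 0.67 already needs an estimate of 0.67 × exp(1.968 × 0.1212) ≈ 0.85.

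**The case against.** The strongest reply is that nothing printed is miscalculated. The paragraphs are introduced by type of comparison, and the reference-strain inputs are said to apply to each comparison, so a careful reader can see what the figures are. The sequence is set out openly a few sections earlier. Group size rests on safety, and estimates with confidence intervals are planned for every primary and secondary estimand, so a broken chain does not hide the data. A statistical analysis plan, not available here, may also give sequence-level power.

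Much of this stands. A reader might infer an arithmetic error, but step 1 of the working rules that out. A reader might also infer that 150 per group is too few or that the order is wrong. The documents do not support that, because the sample size is not justified by these powers and a fixed sequence is a valid way to control type I error. The correlations and the common GMR are assumptions, so the simulated figures are illustrative.

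What does not stand is that the partial labelling is enough. The sentences say what the study has or will have, and the 230-participant subset is chosen to evaluate these very objectives. Under the written rule, the chance of declaring the later objectives is lower at every correlation tried.

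**Conclusion.** The point holds as a stated power that the written design does not deliver. The printed figures are correct as single-comparison powers.

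The gap depends on the step and the scenario:

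- **First objective:** small, 87-89% against 91.5% at GMR 1.5.
- **G5vG1B:** about 20-30 points below 90.9% at GMR 1.5, 13-16 points at GMR 2.0, and about 6 points at GMR 2.0 with 78% seroresponse.
- **'Super' superiority at GMR 2.0 with 70% seroresponse:** about 9-17 points below 65.7% for G4vG1B, 19-29 for G6vG1C, 26-35 for G5vG1C and 32-40 for G3vG1B.

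Two misreadings should be avoided. G5vG1C closes the 'super' superiority line but is only step 8; the last 'super' test is G3vG1B at step 10. The 61-71% for G5vG1B and the 31-40% for G5vG1C belong to different true GMRs and do not describe one scenario.

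The direction of the result does not depend on the assumed correlations, but the exact values do. They also rest on a common true GMR across variant arms, a shared Group 1 and a reference-strain GMR of 1.

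**What to change.** In section 10.11.9.5, state that 91.5%, 94.9%, 90.9% and 65.7% are powers for a single comparison and ignore both the joint requirement and the sequence in section 10.11.9.1.3. Beside them, give the simulated power to declare each objective under that rule. For each figure, state the true GMR, seroresponse rates and correlations assumed, and show a range where the correlations are unknown.

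The cost is one simulation and a few sentences. Sample size, sequence, visits and assays stay as they are. The only downside is that the stated powers become less favourable.

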10.12. Appendix 12: Substudy F

10.12.1. Substudy Summary

10.12.1.1. Substudy Synopsis

See Section 1.1 for a synopsis of Substudy F.

10.12.1.2. Schema

| Visit Number | 701 | 702 | 703 | 704 | 705 |
|---|--|--|---|--|--|
| Visit Description | 4 th Dose of BNT162b2 or BNT162b2 OMI or Combination BNT162b2/BNT162b2 OMI | 7 Days After 4 th Vaccination | 1 Month After 4 th Vaccination | 3 Months After 4 th Vaccination | 6 Months After 4 th Vaccination |
| Participants having received 3 prior doses of 30 µg BNT162b2 ≥4 months prior to | | | | | |
| randomization | 30-μg OR 60-μg dose | | | | |
| Blood draw for immunogenicity assessments ^a | ~25 mL | ~25 mL | ~25 mL | ~25 mL | ~25 mL |
| Blood draw for additional laboratory testing ^b | ~35 mL | ~35 mL | ~35 mL | ~35 mL | ~35 mL |

a. ~11 mL for Pfizer central laboratory testing, ~11 mL for Sheba laboratory testing, and ~3 mL for BioNTech laboratory testing. See Section 10.12.8.2.

b. ~35 mL collected for PBMC for Sheba and BioNTech as described in Section 10.12.8.2.

10.12.1.3. Schedule of Activities for Substudy F

| Visit Number | 701 | 702 | 703 | 704 | 705 | Unplanned |
|--|--------------------|--|---|---|---|--|
| Visit Description | Vaccination | 1-Week Follow-Up Visit After Vaccination | 1-Month Follow-Up Visit After Vaccination | 3-Month Follow-Up Visit After Vaccination | 6-Month Follow-Up Visit After Vaccination | Potential COVID-19 Illness Visit ^a |
| Visit Window (Days) | Day 1 ^b | 6 to 8 Days After Visit 701 | 28 to 35 Days After Visit 701 | 85 to 95 Days After Visit 701 | 175 to 189 Days After Visit 701 | Optimally Within 3 Days After Potential COVID-19 Illness Onset |
| Obtain informed consent | X | | | | | |
| Perform SARS-CoV-2 antigen test | X | | | | | |
| Assign participant number | X | | | | | |
| Obtain demography and medical history data | X | | | | | |
| Perform clinical assessment ^c | X | | | | | |
| Measure height and weight | X | | | | | |
| Measure temperature (body) | X | | | | | |
| Perform urine pregnancy test (if appropriate) | X | | | | | |
| Confirm use of contraceptives (if appropriate) | X | X | X | | | |
| Collect nonstudy vaccine information | X | X | X | X | X | |
| Collect prohibited medication use | | X | X | X | X | X |
| For participants who are HIV-positive, record latest CD4 count and HIV viral load | X | | X | X | X | |
| Confirm eligibility | X | | | | | |
| Review temporary delay criteria | X | | | | | |
| Collect blood sample for immunogenicity assessments ^d | ~25 mL | ~25 mL | ~25 mL | ~25 mL | ~25 mL | |
| Collect blood sample for additional laboratory testing ^e | ~35 mL | ~35 mL | ~35 mL | ~35 mL | ~35 mL | |
| Obtain nasal (midturbinate) swab | X | | | | | X |
| Obtain the participant's vaccine vial allocation using the IRT system | X | | | | | |
| Administer study intervention | X | | | | | |
| Assess acute reactions for at least 30 minutes after study intervention administration | X | | | | | |

| Visit Number | 701 | 702 | 703 | 704 | 705 | Unplanned |
|--|--------------------|--|---|---|---|--|
| Visit Description | Vaccination | 1-Week Follow-Up Visit After Vaccination | 1-Month Follow-Up Visit After Vaccination | 3-Month Follow-Up Visit After Vaccination | 6-Month Follow-Up Visit After Vaccination | Potential COVID-19 Illness Visit ^a |
| Visit Window (Days) | Day 1 ^b | 6 to 8 Days After Visit 701 | 28 to 35 Days After Visit 701 | 85 to 95 Days After Visit 701 | 175 to 189 Days After Visit 701 | Optimally Within 3 Days After Potential COVID-19 Illness Onset |
| Explain/review participant communication methods (including for e-diary completion), assist the participant with downloading the app, or issue provisioned device, if required | X | | | | | |
| Provide/ensure the participant has a thermometer and measuring device | X | | | | | |
| Review reactogenicity e-diary data (daily review is optimal during the active diary period) | $X \rightarrow$ | $X \rightarrow$ | | | | |
| Review ongoing reactogenicity e-diary symptoms and obtain stop dates | | X | X | | | |
| Collect AEs and SAEs as appropriate | X | X | X^{f} | X ^f | X^{f} | X |
| Collect e-diary or assist the participant to delete application | | | | | X | |
| Collection of COVID-19–related clinical and laboratory information (including local diagnosis) | | | | | | X |
| Provide/ensure the participant has a nasal self-swab kit and instructions on self-collection of nasal swabs | X | X | X | X | | |

Abbreviations: HIV = human immunodeficiency virus; IRT = interactive response technology.

- a. The COVID-19 illness visit may be conducted as an in-person or telehealth visit.
- b. The visit may be conducted across 2 consecutive days; if so, all steps from assessing the inclusion and exclusion criteria onwards must be conducted on the same day.
- c. Including, if indicated, a physical examination.
- d. ~11 mL for Pfizer central laboratory testing, ~11 mL for Sheba laboratory testing, and ~3 mL for BioNTech laboratory testing. See Section 10.12.8.2.
- e. ~35 mL collected for PBMC for Sheba and BioNTech as described in Section 10.12.8.2.
- f. Any AEs occurring up to 48 hours after the blood draw must be recorded (see Section 8.3.1).

